15.2 Planned recruitment rate

The estimated planned recruitment rate is two to three patients per month. Since the inclusion criteria is all adult patients predicted stay of 72 hours in critical care, we are aiming to finish the study over a 12–15-month recruitment period. The CI has a track record of leading research studies like ASICS ⁴⁴ and PROSPER. The study coordinator is responsible for driving recruitment and support and encourage the delivery team to meet the recruitment target.

15.3 End of trial (EOT) definition

The EOT is defined as the date the last patient sample analysed. The CI is delegated the responsibility of submitting the EOT notification to REC and MHRA once reviewed by sponsor. The EOT notification must be received by REC and MHRA within 90 days of the end of the trial. If the study is ended prematurely, the CI will notify the Sponsor, REC, and MHRA within 15 days, including the reasons for the premature termination.

15.4 Statistical Analysis

After the completion of the dose-escalation (stopping rule met), the maximum tolerable dose (primary outcome) will be calculated using an isotonic regression considering the DLT events across all doses³⁵. This computation is implemented by the "BOIN" app available at http://www.trialdesign.org. The maximum tolerable dose is selected as the dose for which the isotonic estimate of the toxicity rate is \leq 0.359 and closest to the target toxicity rate (0.30). If there are ties, the higher dose level is selected when the isotonic estimate is lower than the target toxicity rate and the lower dose level is selected when the isotonic estimate is greater than or equal to the target toxicity rate.

Analyses of the exploratory outcomes will estimate dose-response effects of Omegaven, using the data from the control group as a comparator. Analyses of the exploratory clinical and laboratory outcomes will primarily use descriptive statistics. Quantitative data will be summarised by group, using descriptive statistics including mean (standard deviation) or median (interquartile range), as appropriate. Categorical data will be summarised by group, using frequencies and percentages. Further exploratory analysis of the laboratory outcomes will use repeated measures analysis of covariance including data at all follow-up time-points to compare each dose level with concurrently randomised controls, adjusting for baseline values. Differences between groups will be described using point estimates and 95% confidence intervals.

Given that the majority of data collection will occur in hospital, we anticipate a low missing data rate. A full statistical analysis plan will be drawn up prior to analysis, and will include handling of missing data, outliers, protocol violations.

15.5 Summary of baseline data and flow of participants

Reporting of trial results and flow of participants will be in accordance with the CONSORT Dose-finding extension (CONSORT-DEFINE) guidance.⁴⁵

15.6 Analysis of participant populations

Analyses will include all participants who receive at least one dose of Omegaven.

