2.6 Trial design

To improve transparency, completeness, reproducibility and trial usefulness of this early phase dose-finding trial, the Standard Protocol Items: Recommendations for Interventional Trials Dose-finding Extensions (SPIRIT-DEFINE) guideline ²⁵ has been followed. This is a dose-escalation, randomised controlled trial, where critically ill patients will receive either Omegaven or standard care for 10 days or until hospital discharge, whichever is sooner. The Bayesian Optimal Interval (BOIN) design is being used to specify the dose-escalation/ de-escalation decision strategy whereby the observed dose-limiting toxicity (DLT) at each dose level is

compared with a pair of escalation and de-escalation boundaries optimised to minimise the risk of patients receiving overly toxic or subtherapeutic doses.²⁶ The BOIN design implemented in HIPPO is similar to the traditional 3+3 design but provides more flexibility and possesses superior operating characteristics that are comparable to those of more complex model-based designs.²⁷

Dose-limiting toxicity assessment

DLT events and assessments will be treated separately from the overall pharmacovigilance described in section 13.0.

Patients will be screened for DLT events once a day (this can be at any point during a 24-hour period) from the start of the intervention until five hours after the completion of the last dose or hospital discharge, whichever occurs first. DLT event screening will also occur in control patients from days 1-11 to compare the event rates with the intervention arm. Screening for DLT events will occur by reviewing routinely collected clinical laboratory tests and clinical examination in the first place. Blood tests include electrolytes, glucose, serum creatinine, liver enzymes (serum ALT, AST, ALP, y-glutamyl transpeptidase) and total serum bilirubin, serum triglycerides, blood count (leukocytes, platelets, red blood cells, neutrophils, lymphocytes, monocytes, eosinophils, basophils, and nucleated red blood cell count) and coagulation measures (prothrombin time, PTR/INR, activated partial thromboplastin time), and acid-base metabolism. If these measures are not available routinely, they will be mandated by the research team. Similarly, daily vital sign measurements (heart rate, blood pressure, body temperature, fluid balance and respiratory rate) will be taken by the research team, if not performed as part of routine care. These results will be noted in the Case Report Form (CRF).

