Haemolysis	Widespread erythrocyte cell membrane destruction	Haemoglobin measured daily. Treating clinician requests haemolysis screen if indicated. -	- Laboratory evidence of haemolysis (e.g., direct antiglobulin test; schistocytes; decreased haptoglobin) AND - Loss of > 2 g haemoglobin within 24 hours (2 blood tests closest to 24 h apart) AND - Transfusion or medical intervention (i.e. steroids) indicated AND - No other potential cause than the intervention	Evidence of haemolysis within 24 hours of Omegaven infusion Transfusions that occur within 24 hours of diagnosis of haemolysis	- Document and contact CI
Hyper-triglyceridaemia	Elevated levels of triglycerides in blood	- Measured daily	- Triglycerides > 530.97 mg/dl (6 mmol/l) ³⁰	If occurs at any point during the infusion or within five half-lives (5 hours) of finishing the infusion	Stop infusion Document and contact CI
Reticulocytosis	Increase in circulating reticulocytes (immature red blood cells) as sign of accelerated erythrocyte production	- Measured daily.	Reticulocytes >100 x10 ⁹ /I ³⁴ AND No other potential cause than the intervention AND Need for transfusion within 24 hours of diagnosis	- Need for transfusion within 24 hours of diagnosis	- Document and contact CI
Thrombocytopenia	Deficiency of blood platelets	- Measured daily.	 Platelets <50 x10⁹ with requirement of platelet transfusion AND 	Within 24 hours of infusionTransfusions that occur within 24 hours	- Document and contact CI

HIPPO V3.0 14/02/2025 Page 19 of 62

			Absence of other causes of thrombocytopenia such as therapeutic agents (e.g. heparin), chronic diseases	of diagnosis of thrombocytopenia	
Thrombophlebitis	Inflammation in the vein in the presence of an intravenous catheter	 Identified on clinical examination by staff or by patient if conscious. Absence of documentation will be considered to indicate no concern. 	 Grade 3 (Pain at the puncture site with erythema, hardening and a palpable venous cord) OR Grade 4 (Pain at the puncture site with erythema, hardening and a palpable venous cord that is > 1 cm, with purulent discharge) 	If occurs within 24 hours of any Omegaven infusion, specific to the cannula used to infuse Omegaven.	- Document and contact CI

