5.0 Participant allocation

Since the trial involves an IMP that is unlicensed in UK, the PI or delegated doctors will be required to confirm eligibility of patients identified by the research team in the medical notes prior to approach. Following written informed consent, the patient will be randomised to either the standard care or Omegaven arm in blocks of 12 patients per dose-escalation phase. All randomised patients will be recorded on the study enrolment log with their trial ID.

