15.0 Statistical and data analysis

15.1 Sample size calculation

A total of 36 participants will be recruited (randomised 1:3 control:intervention). The number of participants treated on each dose of Omegaven will be determined by the escalation / deescalation rule specified in the BOIN design shown in Figure 2 and Table 1, which aims to exclude a toxicity rate of ≥ 30%. The minimum number of participants to be treated on a single dose is nine and the maximum is 27. Assuming mortality of approximately 20-30% in critically ill patients, we will replace up to a maximum of three patients in each study phase in case of patient death, or withdrawal. There is no formal assessment of sample size required for a phase I dose escalation trial, however 36 participants (nine control and 27 intervention) will be sufficient to provide pilot data on the exploratory outcomes. A published study with eight patient samples per group enabled examination of the p38 inhibitor and identification of a doubling in proliferation and cytotoxicity as measured by granzyme and perforin expression using nine patients per group would provide almost 80% power to detect a mean difference of 12 in %CD107a CD8+ EMRA T cells (assuming SD=6 and α=0.05) (unpublished data, [name])¹⁵. Early phase trials often use less conservative type I error rates as they can be considered screening studies to inform a future definitive trial; with this sample size the trial would have 87.4% power for α =0.1 and 94.4% for α =0.2 using the parameters given above.

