15.9 Safety analysis

Frequencies and type of AEs will be recorded for each randomised group (control and intervention), and each dose level of Omegaven.

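### Section 15.6 states one analysis population that no control can enter, and section 2.6 compares event rates with controls under a DLT definition that no control can meet as written; the MTD is unaffected.

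*Protocol*

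**What the plan says.** Section 15.6 consists of one sentence on who is analysed: "Analyses will include all participants who receive at least one dose of Omegaven". It is not limited to the DLT or MTD analysis, and the protocol states no other population.

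Other sections plan analyses that need controls:

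- Section 15.4: exploratory outcomes are analysed "using the data from the control group as a comparator", and the laboratory model is "to compare each dose level with concurrently randomised controls".
- Section 15.9: "Frequencies and type of AEs will be recorded for each randomised group (control and intervention), and each dose level of Omegaven".
- Section 2.4: the immune and metabolic data are to be read against control blood samples.
- Section 2.6: "DLT event screening will also occur in control patients from days 1-11 to compare the event rates with the intervention arm".

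Section 2.6 also sets the DLT definition. Even a potential DLT has to be attributable to Omegaven. It counts only if relatedness is rated definite or probable/likely. Table 1 adds a time window to each event. For thrombophlebitis the window reads: "If occurs within 24 hours of any Omegaven infusion, specific to the cannula used to infuse Omegaven". The adjudication panel is to be blinded to arm.

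**The concern.** There are two separate defects.

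The first is the population. A control never receives Omegaven (section 7.0), so a rule that admits only dosed participants leaves out the whole control arm. An analyst who follows 15.6 cannot produce the comparisons in 15.4 and 15.9. An analyst who follows 15.4 and 15.9 departs from the only stated population.

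The second is the control event rate. Section 1.2 includes the control group to show what outcomes to expect without the drug, which matters in an ICU population where falling platelets or raised triglycerides also occur without Omegaven. The events to be compared are defined by reference to a drug and an infusion that controls do not have. A zero that arises from the definition, set beside the treated rate, would make every DLT on Omegaven look like an excess over background. If the event definition or the population is instead chosen once control data have been seen, the choice is post hoc.

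**Working it through.** **Step 1: who is in the 15.6 set.** Section 15.1: "A total of 36 participants will be recruited (randomised 1:3 control:intervention", that is 9 controls and 27 on Omegaven. If every Omegaven patient is dosed and replacements are ignored, the 15.6 set is 27 of 36, with 0 of 9 controls. The excluded share is 9/36 = 25% of participants and 100% of controls.

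**Step 2: the power figures in 15.1 need controls.** Section 5.0 allocates "in blocks of 12 patients per dose-escalation phase", which at 1:3 is nominally 9 treated and 3 control per phase. For a two-sided two-sample t-test, the noncentrality is difference / (SD × √(1/n1 + 1/n2)), with n1 + n2 − 2 degrees of freedom. Section 15.1 gives a difference of 12 and an SD of 6.

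- 9 versus 3: 12 / (6 × √(1/9 + 1/3)) = 3.0, df 10.
- 9 versus 9: 12 / (6 × √(1/9 + 1/9)) = 4.24, df 16.

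| α | Stated in 15.1 | 9 vs 3 | 9 vs 9 |
|---|---|---|---|
| 0.05 | almost 80% | 77.1% | 97.8% |
| 0.1 | 87.4% | 87.4% | 99.2% |
| 0.2 | 94.4% | 94.4% | 99.8% |

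The last two stated figures reproduce exactly for one dose cohort against three controls, and the first is a loose rounding of 77.1%. They do not reproduce for nine per group, which is how 15.1 words it. The power statement therefore presupposes the controls that 15.6 leaves out. With no controls there is no contrast to power.

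**Step 3: can a control meet Table 1?**

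| Event | What ties it to Omegaven |
|---|---|
| Haemolysis | Window from Omegaven infusion; intervention the only possible cause |
| Hyper-triglyceridaemia | During the infusion or within 5 hours of its end |
| Reticulocytosis | No infusion window; intervention the only possible cause |
| Thrombocytopenia | Within 24 hours of infusion |
| Thrombophlebitis | Within 24 hours of infusion, at the Omegaven cannula |
| Urticaria | Within one hour of Omegaven infusion |
| Other | During the infusion or within 5 hours of its end; suspected link to Omegaven |

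Three rows (triglycerides, thrombocytopenia, Other) say infusion without naming the drug, but in context it can only be Omegaven. Six of seven events thus need an infusion, and the seventh needs the intervention as sole cause. The relatedness rating in Table 2, which relies on timing relative to drug intake, comes on top. No substitute reference time is given for controls.

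**Step 4: what a zero would mean.** Even a genuine 0/9 has an exact two-sided 95% upper limit of 1 − 0.025^(1/9) = 33.6%. For 0/3 in one phase it is 1 − 0.025^(1/3) = 70.8%. A zero fixed by definition carries no information on background at all. The protocol gives no background rate. Assuming 5% to 30% under an arm-neutral definition, the expected number of control events is 9 × 0.05 = 0.45 to 9 × 0.30 = 2.7. The chance of at least one is 1 − 0.95^9 = 37% to 1 − 0.70^9 = 96%.

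**The case against.** The strongest reply is that the intent is clear. Sections 2.4, 15.4 and 15.9 say plainly that controls are analysed, and 15.6 says that dosed participants are included, not that only they are. The likeliest explanation is a treated-set rule meant for the DLT/MTD analysis and written too broadly. A reader might infer from 15.6 that the control arm cannot be analysed. The documents do not support that, and this part of the reply stands. What remains is a contradiction: 15.6 is the sole stated population and is wrong for every analysis that involves controls. Section 15.4 defers further detail to a statistical analysis plan, but that does not remove it, because the protocol has fixed the population itself.

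On the second defect, section 2.6 speaks of comparing event rates, not adjudicated DLT rates, and describes two steps: a Table 1 event is identified, then relatedness is judged. Thresholds such as triglycerides above 6 mmol/l can be seen in controls, so a comparison of first-step events is workable. A panel that does not know the arm could also rate a control event as probable. A reader might infer that the control rate must be 0/9. That holds only under strict application, so undefined is the accurate word. The two-step reading still does not rescue the text, because section 2.6 makes attribution to Omegaven part of even a potential DLT.

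On blinding, the protocol does not say who applies the time windows or what the panel sees. It is plausible, but not shown, that infusion times would reveal the arm.

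**Conclusion.** The point holds as an internal contradiction plus an undefined comparison. Section 15.6 as worded leaves out 9 of 36 participants, all of them controls, and conflicts with four sections that plan to use them. No control can meet any of the seven Table 1 events as written, so the event-rate comparison in 2.6 has no usable definition.

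The reach is limited. A reader might infer that dose selection is compromised, but it is not. The DLT rate in section 2.6 counts only evaluable patients treated at the current dose, and the isotonic regression in 15.4 pools DLTs across doses, so controls enter neither. The exploratory laboratory and clinical outcomes, the AE tables by arm and the background-event comparison are affected. These are mainly descriptive, but supplying them is the stated reason for having a control group.

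The counts assume the planned 27 and 9. The 5% to 30% background range is an assumption used only for illustration.

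**What to change.** 1. **Section 15.6.** Limit the at-least-one-dose set to the DLT/MTD analysis. State that the AE and exploratory analyses include all randomised participants, controls included.
   - Report AEs in the Omegaven arm by dose received, and show patients randomised to Omegaven but never dosed separately.
   - Laboratory models use all participants with available data.
   - Do not make clinical outcomes conditional on having a follow-up sample. The first is on day 5, and 15.1 assumes 20-30% mortality, so such a condition could remove early deaths from the mortality and free-day summaries.
2. **Section 2.6.** Define the control comparison. In both arms, over days 1-11, count patients with an event that meets the Table 1 laboratory or clinical threshold, without the attribution, infusion-time or cannula clauses. Show Other on its own row, because its notification depends on suspicion of Omegaven and the care team knows the arm (section 8.4).
3. **Reporting.** Present this count beside the attributed DLTs, which remain the sole input to BOIN.

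The cost is protocol wording and one extra table. Sections 8.1 and 8.2 already schedule daily DLT review to day 11 for all participants, so no new data are needed. Settle the wording before control events are adjudicated.

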15.7 Primary endpoint analysis

Described in section 15.4.

15.8 Secondary endpoint analysis

N/A.

15.9 Safety analysis

Frequencies and type of AEs will be recorded for each randomised group (control and intervention), and each dose level of Omegaven.

15.10 Subgroup analyses

There is no planned subgroup analysis.

15.11 Adjusted analysis

As described in section 15.4 the exploratory analysis of the laboratory outcomes will adjust for baseline values in the analysis of covariance. There will be no additional adjustments.

15.12 Interim analysis and criteria for the premature termination of the study

There will be no interim analysis. However, there is a safety assessment, before every dose-escalation, which might trigger staying on the same dose, dose de-escalation or termination.

15.13 Procedure(s) to account for missing or spurious data

There will be no imputation of missing data on the exploratory outcomes. The reasons for missing data will be recorded in the CRF, for e.g. withdrawal etc.

15.14 Other statistical considerations

As described in section 9.0 if a patient withdraws, dies, or is excluded by their Intensive Care Consultant with clinical responsibility for patient care or the study team during the 10-day dosing period, they will be replaced. Three such patients, in case of withdrawal or death, will be replaced in each study phase.

16.0 Data handling and record keeping

16.1 Source data and source documents

Source data is defined as all information in original patient records and certified copies of original records of clinical findings, observations, or other activities in a clinical trial necessary

for the reconstruction and evaluation of the clinical investigation. Source data are contained in source documents (original records or certified copies). Only members of the direct care team are entitled to have access to patients' medical records before consenting to the trial. A source data agreement will be in place for the site. Direct access will be granted to authorised representatives from the sponsor, host institution, and the regulatory authorities to permit study-related monitoring, audits, and inspections.

16.2 Case Report Forms (CRFs)

A summary of the data collection points and times can be found in section 8.2 Research staff at each hospital will be responsible for the completion of the electronic case report form for the duration of the study. Site will be provided with a paper data collection tool that matches the electronic Case Report Form (eCRF) however, it is not compulsory to complete this if it has been completed electronically.

The eCRF and randomisation system will be custom designed by Queen Mary University of London using a bespoke clinical trial database system called 'Datameld' and will be hosted on a secure server in accordance to Sponsor requirements. A requirement specifications document will be created detailing these aspects of the database.

16.3 Data capture

Data required for the trial will be collected by the delegated investigators or the research nurses and captured in an eCRF. Source data will be obtained from the sites medical notes including the electronic patient record and in accordance with the source data agreement at each site. Source data will be reviewed as part of the source data verification during site monitoring.

16.4 Transferring and transporting data

All data must be handled in accordance with the Data Protection Act (2018) and General Data Protection Guidelines. No data will be transferred outside of the UK. Identifiable information will not be stored, transported on any portable device (e.g. laptops, memory sticks) unless it is encrypted and will not be sent electronically; if it is not subject to end-to-end encryption. Barts Health Participant Identifiable Data (PID) will not be taken out of Barts Health without participant consent.

16.5 Data Management

A full data management plan will be developed to describe in detail the methods of data management. All participant data collected will be entered onto a secure electronic data entry system. The site Principal Investigator will oversee and be responsible for data collection, quality and recording. Collection of data can be delegated (as per the Delegation Log) by the site Principal Investigator to qualified members of the research team. Data entered onto the secure electronic data entry system will undergo validation checks for completeness, accuracy and consistency of data. The electronic storage will be located on a restricted area of the file server. Submitted data will be stored securely against unauthorised manipulation and accidental loss. Queries on incomplete, inaccurate or inconsistent data will be sent to the local research team at participating sites for resolution. Security of the electronic data entry system is maintained through usernames and individual permissions approved centrally by the HIPPO trial mangers. Central back-up procedures are in place. Storage and handling of confidential trial data and documents will be in accordance with the Data Protection Act (2018) and General Data Protection Regulations. Representatives of the trial management team will require access to patient notes for quality assurance purposes and source data verification, but patients' confidentiality will be respected at all times. In the case of special problems and/or competent authority queries, it is also necessary to have access to the complete trial records, provided that patient confidentiality is protected.

